##### **9.1.5.1 Discontinuation During the Run-in Period**

Subjects who prematurely discontinue study drug treatment during the TEZ/IVA Run-in Period will not be randomized or participate in the Treatment Period. These subjects will complete an ETT Visit and Safety Follow-up Visit (as applicable; see Section 9.1.5). The Safety Follow-up Visit will be their last visit in the study.

##### **9.1.5.2 Discontinuation During the Treatment Period**

Subjects who prematurely discontinue study drug treatment during the Treatment Period will continue to complete all scheduled study visits following completion of the ETT Visit, as

detailed in [Table 3-2](#). These subjects will complete an ETT Visit and Safety Follow-up Visit (as applicable; see [Section 9.1.5](#)).

### **9.1.6 Lost to Follow-up**

A subject will be considered lost to follow-up if both of the following occur:

- The subject misses 2 consecutive study visits (telephone contact and/or clinic visit) and is subsequently unable to be contacted by telephone (3 documented attempts by telephone within 2 weeks following the second missed visit).
- The subject does not respond within 2 weeks to a registered letter sent after the 3 attempted telephone contacts.

### **9.1.7 Completion of Study Participation**

Completion of study participation for each individual subject is defined as one of the following:

- For subjects who complete the Treatment Period and enter an open-label study within 28 days of the Week 24 Visit: the Week 24 Visit
- For subjects who complete the Treatment Period and do not enter an open-label study within 28 days of the Week 24 Visit: the Safety Follow-up Visit
- For subjects who prematurely discontinue study drug treatment during the Treatment Period but do not withdraw consent (and assent, as applicable): The latest of the Week 24 Visit, ETT Visit, or Safety Follow-up Visit (if required)
- For subjects who prematurely discontinue study drug treatment during the TEZ/IVA Run-in Period but do not withdraw consent (and assent, as applicable): the ETT or Safety Follow-up Visit (if required)
- For subjects who withdraw consent or assent: date of withdrawal of consent or assent, whichever is earlier ([Section 9.9](#))

If subjects are lost to follow-up ([Section 9.1.6](#)), the date of completion of study participation will be defined as the date of the last contact.

The end of study is defined in [Section 13.2.8](#).

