**Table 3-1 Study VX18-445-109: Screening**

Event/Assessment	Screening Visit Day -56 to Day -29	Comments
ICF and assent (when applicable)	X	
Inclusion and exclusion criteria review	X	
Demographics	X	
Medical history	X	
CFQ-R	X	Completed before the start of any other assessments (except signing ICF) scheduled for that visit.
CFTR genotype	X	If the screening CFTR genotype result is not received before enrollment, a previous CFTR genotype laboratory report may be used to establish eligibility. Subjects who have been enrolled and whose screening genotype does not confirm eligibility must be discontinued from the study.
FSH	X	Measured for any suspected postmenopausal female with at least 12 months of continuous spontaneous amenorrhea.
Serum pregnancy test (all female subjects)	X	
Hematology	X	
Coagulation	X	
Serum chemistry	X	
Urinalysis	X	
Weight and height	X	Measured with shoes off.
Ophthalmologic examination	X	Only conducted for subjects who are <18 years of age on the date of informed consent.
Complete physical examination	X	
Vital signs and pulse oximetry	X	Collected after the subject has been at rest for at least 5 minutes.
Standard 12-lead ECG	X	Performed after the subject has been at rest for at least 5 minutes.
Spirometry	X	Performed pre- or post-bronchodilator.
Medications review	X	
Sweat chloride	X	
AEs and SAEs	Continuous from signing of ICF through Safety Follow-up Visit	
AE: adverse event; CFQ-R: Cystic Fibrosis Questionnaire-Revised; FSH: follicle stimulating hormone; ICF: informed consent form; SAE: serious adverse event		

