**Table 3-2 Study VX18-445-109: Treatment Period and Safety Follow-up Visit**

Event/ Assessment a	TEZ/IVA Run-in Period (4 weeks)		Treatment Period (24 weeks)								ETT Visit b	Safety Follow-up Visit c (28 ± 7 Days After Last Dose of Study Drug)	Comments
	Day -28 ± 1 day	Day -14 (Day -15 to Day -3)	Day 1 d	Day 15 ± 3 days	Week 4 ± 5 days	Week 8 ± 5 days	Week 12 ± 5 days	Week 16 ± 5 days	Week 20 ± 5 days	Week 24 ± 5 days			
Clinic visit	X	X	X	X	X	X		X		X	X	X	
Telephone contact							X		X				Assess the subject's status, any AEs, concomitant medications, treatments, and procedures.
Inclusion and exclusion criteria confirmation	X												
CFQ-R			X		X	X		X		X	X	X	Completed before any other assessments scheduled at relevant visits (Section 11.4.1).
Weight and height	X		X	X	X	X		X		X	X	X	Measured with shoes off. Height will only be collected for subjects ≤21 years of age on the date of informed consent (Section 11.4.3).
Ophthalmologic examination										X	X		Subjects <18 years of age on the date of informed consent and who completed at least 12 weeks of study drug treatment will have a single ophthalmologic examination at either the ETT or Week 24 Visit, whichever comes first (Section 11.5.6).
Complete physical examination	X		X		X					X	X		Symptom directed physical examinations may be performed at any time if deemed necessary by the investigator (Section 11.5.3).

a All assessments will be performed before dosing unless noted otherwise.

b If a subject prematurely discontinues study drug treatment, an ETT Visit should be scheduled as soon as possible after the decision to discontinue treatment. Subjects who prematurely discontinue treatment during the Treatment Period will continue to complete all scheduled study visits for assessments following completion of the ETT Visit.

c The Safety Follow-up Visit is required for all subjects, unless the subject completes the Week 24 Visit and has enrolled in a separate open-label study within 28 days after the last dose of study drug. If an ETT Visit occurs 3 weeks or later following the last dose of study drug, then the ETT Visit replaces the Safety Follow-up Visit.

d To enter the Treatment Period, conditions for entry must be satisfied.

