Treatment and procedures review	Continuous from signing of ICF through completion of study participation											Completion of study participation is defined in Section 9.1.7.	
AEs and SAEs	Continuous from signing of ICF through completion of study participation											Completion of study participation is defined in Section 9.1.7.	
AE: adverse event; CFQ-R: Cystic Fibrosis Questionnaire-Revised; ETT: Early Termination of Treatment; ICF: informed consent form; IVA: ivacaftor; SAE: serious adverse event; TEZ: tezacaftor													

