##### **13.1.1.3 Documentation of Adverse Events**

All AEs will be collected from the time the ICF is signed until the subject completes study participation, as defined in Section [9.1.7](#)

All subjects will be queried, using nonleading questions, about the occurrence of AEs at each study visit. When possible, a constellation of signs and/or symptoms will be identified as 1 overall event or diagnosis. All AEs for enrolled subjects will be recorded in the CRF and source document. AEs for subjects who are screened but not subsequently enrolled will be recorded only in the subject's source documents. The following data will be documented for each AE:

- Description of the event

- Classification of “serious” or “nonserious”
- Date of first occurrence and date of resolution (if applicable)
- Severity
- Causal relationship to study drug(s)
- Action taken
- Outcome
- Concomitant medication or other treatment given

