#### 13.1.2.2 Reporting and Documentation of Serious Adverse Events

All SAEs that occur after obtaining informed consent and assent (where applicable) through the completion of study participation, regardless of causality, will be reported by the investigator to Vertex GPS **within 24 hours of identification**. In addition, all SAEs that occur after the completion of study participation and are considered related to study drug(s) will be reported to Vertex GPS **within 24 hours of identification**.

For SAEs that occur after obtaining informed consent and assent (where applicable) through the completion of study participation, the SAE Form will be completed for new/initial events as well as to report follow-up information on previously reported events. Investigators are asked to report follow-up information as soon as it becomes available to ensure timely reporting to health authorities.

Please send completed SAE Forms to Vertex GPS via:

Email: [REDACTED] (preferred choice)

Fax: [REDACTED]

For technical issues related to submitting the form, contact telephone: [REDACTED]

SAEs that occur after the completion of study participation and are considered related to study drug(s) will be recorded on the Vertex Clinical Trial Safety Information Collection Form (hereafter referred to as the “SAE Form”) using a recognized medical term or diagnosis that accurately reflects the event. SAEs will be assessed by the investigator for relationship to the investigational study drug(s) and possible etiologies. On the SAE Form, relationship to study drug(s) will be assessed only as related (includes possibly related) or not related (includes unlikely related), and severity assessment will not be required. For the purposes of study analysis, if the event has not resolved at the end of the study reporting period, it will be documented as ongoing. For purposes of regulatory safety monitoring, the investigator is required to follow the event to resolution and report the outcome to Vertex using the SAE Form.

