9 STATISTICAL ANALYSIS

9.1 General Considerations

Continuous variables will be summarized using the following descriptive summary statistics: the number of subjects (n), mean, SD, median, minimum value (min), and maximum value (max).

Categorical variables will be summarized using counts and percentages.

Baseline value, unless otherwise specified, will be defined as the most recent non-missing measurement (scheduled or unscheduled) collected before the first dose of study drug in the Treatment Period (i.e., the Day 1 Visit). For ECG, baseline will be defined as the most recent pretreatment measurement (or the average of triplicate measurements, if the most recent pretreatment measurement is obtained in triplicate) before the first dose of study drug in the Treatment Period (i.e., the Day 1 Visit).

Absolute change from baseline will be calculated as post-baseline value – baseline value.

Relative change from baseline will be calculated as (post-baseline value – baseline value)/baseline value.

The **Treatment-emergent (TE) Period for the Run-in Period** will be from the first dose of study drug in the Run-in Period to (1) the first dose of study drug in the Treatment Period for subjects who complete the Run-in Period and continue to the Treatment Period, or (2) 28 days after the last dose date of study drug in the Run-in Period or date of completion of study participation, whichever occurs first, for subjects who do not continue to the Treatment Period (e.g., subjects who do not meet the conditions to enter the Treatment Period).

The **TE Period for the Treatment Period** will include the time from the first dose date of study drug in the Treatment Period (ELX/TEZ/IVA or placebo + TEZ/IVA) to 28 days after the last dose of the study drug or to the date of completion of study participation, whichever occurs first.

Unscheduled visits: Unscheduled visit measurements will be included in analysis as follows:

- 1) In scheduled visit windows per specified visit windowing rules
- 2) In the derivation of baseline and last on-treatment measurements
- 3) In the derivation of maximum and minimum values during TE period, and maximum and minimum change from baseline values during TE period for safety analyses
- 4) In individual subject data listings as appropriate

Visit windowing rules: The analysis visit windows for protocol-defined visits are provided in [Appendix A](#).

Incomplete/missing data will not be imputed, unless specified otherwise.

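### For subjects who enter the open-label study some days after Week 24, adverse events in the gap are never treatment-emergent and, apart from related SAEs, need not be collected

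*Protocol*

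**What the plan says.** Protocol 9.1.7 gives completers one of two end dates. For those who roll over it is: "For subjects who complete the Treatment Period and enter an open-label study within 28 days of the Week 24 Visit: the Week 24 Visit". For the others, who "do not enter an open-label study within 28 days of the Week 24 Visit: the Safety Follow-up Visit", it is about four weeks later.

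Two other rules depend on that date:

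- **Collection.** Protocol 13.1.1.3: "All AEs will be collected from the time the ICF is signed until the subject completes study participation". The AE row of Table 3-2 agrees: "Continuous from signing of ICF through completion of study participation".
- **Classification.** SAP 9.1 runs the TE Period for the Treatment Period from first dose "to 28 days after the last dose of the study drug or to the date of completion of study participation, whichever occurs first". Protocol 12.3.1 has the same rule.

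The Safety Follow-up Visit falls 28 ± 7 days after the last dose. Footnote c of Table 3-2 waives it for a subject who completes Week 24 and "has enrolled in a separate open-label study within 28 days after the last dose of study drug"; 9.1.4 says the same. After completion of participation, 13.1.2.2 still requires reporting of SAEs considered related to study drug, within 24 hours.

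Two places set a later horizon. The statistical part of the synopsis carries the safety endpoints to the Safety Follow-up Visit, and the AE row of Table 3-1 reads "Continuous from signing of ICF through Safety Follow-up Visit".

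**The concern.** The plan treats the 28 days after the last dose as time at risk: both the TE Period and the timing of the Safety Follow-up Visit use it. The roll-over rule removes most of that window for any subject who does not start the open-label study at once. The end date also depends on something that happens later. While the gap is running, the site cannot know whether participation ended at Week 24 or continues to the Safety Follow-up Visit.

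At stake is the completeness of the off-drug safety record, such as a rash or a transaminase rise with onset in the gap. So is the consistency of the TEAE tables, because the same event is counted or not according to a later roll-over decision. Safety is a secondary objective.

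**Working it through.** The plan states no figure on this point, so there is none to reproduce. The check is day arithmetic on its own definitions.

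**Inputs**
- Week 24 target: Day 169 (SAP Appendix A), visit window ± 5 days (Table 3-2).
- Last randomized dose: the evening before the Week 24 Visit (Table 3-2).
- TE end = min(last dose + 28 days, completion of participation) (protocol 12.3.1, SAP 9.1).
- Completion: the Week 24 Visit for roll-over subjects, the Safety Follow-up Visit for other completers (9.1.7).

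**TE end for a Day 169 visit**
- Last dose = 169 − 1 = Day 168. Last dose + 28 = Day 196.
- No roll-over: the Safety Follow-up Visit falls between Day 168 + 21 = 189 and Day 168 + 35 = 203. TE end = min(196, visit day), which is Day 189 to Day 196.
- Roll-over: TE end = min(196, 169) = Day 169.
- Days cut, at most: 196 − 169 = 27 of the 28 post-dose days, so the TE Period is 27/196 = 13.8% shorter. Against a Safety Follow-up Visit at the earliest allowed day, the cut is 189 − 169 = 20 days.
- At the edges of the window the maximum is unchanged. Visit on Day 164: (163 + 28) − 164 = 27. Visit on Day 174: (173 + 28) − 174 = 27.

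**Time actually affected.** With the first open-label dose on Day E, it is min(E, 196) − 169 days: 0 if E = 169, and at most 27.

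**One event, two classifications.** Take an AE with onset on post-dose day 10, Day 168 + 10 = 178. If the subject never rolls over, it is a TEAE. If the subject enters the open-label study on post-dose day 27 (Day 195), completion is dated to Day 169. The same AE is then post-treatment (protocol 12.3.4.1, SAP 9.4.1) and, if recorded, appears only in the listing.

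**The two 28-day anchors.** Counted from the Week 24 Visit (9.1.7), the last qualifying entry is 169 + 28 = Day 197. Counted from the last dose (Table 3-2, 9.1.4), it is 168 + 28 = Day 196. A subject entering on Day 197 has finished at Week 24 by one rule and still owes a Safety Follow-up Visit by the other.

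**Illustration on assumed inputs.** The only figure here taken from the documents is the 142 planned completers.
- Assume that 80% to 95% roll over with a mean gap of 2 to 10 days. Time affected: 142 × 0.80 × 2 = 227 to 142 × 0.95 × 10 = 1,349 subject-days.
- Assume a 10% to 50% chance *p* of a new AE per 28 days. The chance of one in a gap of *g* days is 1 − (1 − *p*)^(g/28): about 5% to 29% for 14 days and 10% to 49% for 27 days.

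**The case against.** The strongest reply is that little is lost in practice. Until a subject enters the open-label study, the roll-over bullet of 9.1.7 is not met, so a site working in real time would keep recording AEs. On later entry, those events move from the TEAE tables to the listings. Related SAEs stay reportable. Ending the TE Period at completion is an explicit rule on which protocol and SAP agree. Safety is descriptive only, and no efficacy result, alpha or power is touched. The open-label study may also take consent and begin AE collection at or near Week 24.

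Much of this stands, and it rules out several stronger readings:

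- *A reader might infer that gap AEs are not collected at all.* The text supports less: collection of nonserious AEs and unrelated SAEs is not required, and some may be recorded anyway.
- *A reader might infer that a transaminase rise in the Week 24 sample is lost.* It is not. The sample is dated to that visit, 9.8.1 requires confirmatory testing with no condition that participation is ongoing, and 13.1.1.7 follows an AE to its outcome. Only rises with onset in the gap are affected.
- *A reader might infer a bias between arms.* The rule is the same in both arms, and nothing in the documents shows that roll-over or its timing would differ.

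The reply does not remove the core point. Reclassification still makes counting depend on a later decision. Recording by the open-label study, which these documents do not mention, would not restore TE status in this trial's controlled comparison.

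**Conclusion.** The point holds in this limited form. For completers who enter the open-label study after the Week 24 Visit but within 28 days of it, new AEs in the gap are never treatment-emergent, and only related SAEs must be reported. The cut is 0 to 27 post-dose days per such subject, and 0 if open-label dosing starts at Week 24. This does not match the safety horizon in the synopsis.

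The day counts rest only on the documents' definitions. The total effect cannot be computed, because roll-over rate, gap length and the open-label study's AE rules are not given; the subject-day and AE-probability ranges are illustrations. The one-day difference in anchors and the wording of Table 3-1 are small, but they should be settled in the same edit. The primary and key secondary analyses are unaffected.

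**What to change.** Leave the completion date in 9.1.7 as it is. Moving it would also extend the medication restrictions in Table 9-2 and the stable-regimen requirement in 9.5, both of which run to completion of participation.

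1. In protocol 13.1.1.3, protocol 12.3.1 and SAP 9.1, state that for roll-over subjects AE/SAE collection and the TE Period run to the earlier of the first open-label dose and 28 days after the last dose in this study. Carry the same date into the all-cause SAE rule in 13.1.2.2 and the AE row of Table 3-2.
2. Use one anchor for the 28-day count in Table 3-2, 9.1.4 and 9.1.7.
3. Define *enter* and *enrolled* as either consent or first dose.
4. Align the AE row of Table 3-1.
5. If the open-label study does record AEs in the interval, say so.

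**Cost.** Sites record AEs for a short further interval, and a few off-drug AEs enter the TEAE tables. No visit or sample is added. Because concomitant medication is defined by the TE Period while medication review ends at completion, the SAP needs one sentence on medications in the gap.

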## **9.2 Method of Assigning Subjects to Treatment Groups**

Subjects will be randomized (1:1) to the VX-445/TEZ/IVA or TEZ/IVA group. Randomization will be stratified by ppFEV1 determined during the TEZ/IVA Run-in Period (Day -14 assessment; <70 versus ≥70), age at the Screening Visit (<18 versus ≥18 years of age), and whether the subject is receiving CFTR modulator treatment at the Screening Visit (yes versus no). If the Day -14 ppFEV1 value is not valid or not available, the most recent available ppFEV1 value will be used for stratification.

An interactive web response system (IWRS) will be used to assign subjects to treatment. The randomization code list will be produced by Vertex Biometrics or a qualified randomization vendor.

### **9.3 Rationale for Study Elements**

#### **9.3.1 Study Design**

A randomized, double-blind, controlled study design was selected to assess the effects of VX-445/TEZ/IVA while avoiding observer bias. TEZ/IVA is considered an appropriate active control since TEZ/IVA (Symdeko/Symkevi) is approved to treat CF in this patient population.

A 4-week TEZ/IVA Run-in Period was incorporated into this study to establish a reliable on-treatment (TEZ/IVA) baseline for comparison during the Treatment Period.

The study will have a 24-week duration to allow for the collection of controlled efficacy and safety data.

The extent of response to CFTR modulator treatment may depend on the subject's ppFEV1 value (an index of disease severity) before the start of randomized study drug dosing. Some subjects in this study may be receiving treatment with LUM/IVA or TEZ/IVA at screening, while some subjects may not be receiving treatment with CFTR modulators. Therefore, randomization will be stratified by previous CFTR modulator use and ppFEV1 value determined during the TEZ/IVA Run-in Period after at least 13 days of treatment with TEZ/IVA (Day -14 assessment). Randomization will also be stratified by age at screening. This will ensure a balanced evaluation of adult and adolescent subjects.

#### **9.3.2 Study Population**

CF patients with the F/F genotype have continuing unmet needs despite the availability of CFTR modulators, and are expected to respond to a TC regimen of VX-445/TEZ/IVA based on results from Phase 2 and Phase 3 studies in this population.

The VX-445 Phases 2 and 3 clinical safety and efficacy data support the enrollment of subjects ≥12 and <18 years of age in this study.

#### **9.3.3 Study Drug Dose**

##### **VX-445 Dosage**

A VX-445 dose of 200 mg qd will be administered. This is the dosing regimen that was evaluated in Phase 3 studies of VX-445/TEZ/IVA.

##### **TEZ/IVA Dosage**

TEZ will be administered as 100 mg qd and IVA will be administered as 150 mg q12h. This is the approved dosing regimen for Symdeko/Symkevi.

#### **9.3.4 Rationale for Study Assessments**

SwCl, spirometry, and CFQ-R endpoints are widely accepted and generally recognized as reliable, accurate, and relevant to the study of individuals with CF and were evaluated in previous registration studies of CFTR modulators.

All safety assessments are standard measurements for clinical studies in drug development.

## 9.4 Study Restrictions

### 9.4.1 Prohibited Medications

Table 9-2 lists prohibited medications. A non-exhaustive list of study prohibitions and cautions for medication will be provided in the Study Reference Manual.

